8.1 Dose Levels (Based on Adverse Events in Tables 8.2)

Dose Level	Ponatinib
0*	45mg PO once daily
-1	30mg PO once daily
-2	15mg PO once daily

*Dose level 0 refers to the starting dose.

8.2

→ → *Use the NCI Common Terminology Criteria for Adverse Events (CTCAE) version 4.0* unless otherwise specified* ← ←

CTCAE System/Organ/Class (SOC)	ADVERSE EVENT	AGENT	ACTION**
BASED ON INTERVAL ADVERSE EVENT			
Investigations	Neutrophil count decreased ≥ Grade 3	Ponatinib	Omit ponatinib Resume at 45 mg after recovery to ≤ grade 1 Recurrence at 45 mg: Omit ponatinib Resume at 30 mg after recovery to ≤ grade 1 Recurrence at 30 mg: Omit ponatinib Resume at 15 mg after recovery to ≤ grade 1 Recurrence at 15 mg: Discontinue ponatinib

→ → Use the NCI Common Terminology Criteria for Adverse Events (CTCAE) version 4.0* unless otherwise specified ← ←			
CTCAE System/Organ/Class (SOC)	ADVERSE EVENT	AGENT	ACTION**
	Platelet count decreased \geq Grade 3		
Omit ponatinib Resume at 45 mg after recovery to \leq grade 1
 
Recurrence at 45 mg: Omit ponatinib Resume at 30 mg after recovery to \leq grade 1
 
Recurrence at 30 mg: Omit ponatinib Resume at 15 mg after recovery to \leq grade 1
 
Recurrence at 15 mg: Discontinue ponatinib

	Serum amylase increased \geq Grade 3 with no radiographic findings	Ponatinib	
Omit ponatinib Resume at 45 mg after recovery to \leq grade 1
 
Recurrence at 45 mg: Omit ponatinib Resume at 30 mg after recovery to \leq grade 1
 
Recurrence at 30 mg: Omit ponatinib Resume at 15 mg after recovery to \leq grade 1
 
Recurrence at 15 mg: Discontinue ponatinib

	Serum amylase increased \geq Grade 3 with radiographic findings or Grade 4	Ponatinib	
Omit ponatinib Repeat imaging according to clinical care After resolution by imaging, resume at 30 mg after recovery to \leq grade 1
 
Recurrence at 30 mg: Repeat above Resume at 15 mg after recovery to \leq grade 1
 
Recurrence at 15 mg: Discontinue ponatinib

→ → Use the NCI Common Terminology Criteria for Adverse Events (CTCAE) version 4.0* unless otherwise specified ← ←			
CTCAE System/Organ/Class (SOC)	ADVERSE EVENT	AGENT	ACTION**
	Alanine aminotransferase increased (ALT) and/or Aspartate aminotransferase increased (AST) ≥ Grade 3	Ponatinib	Omit ponatinib Resume at 30 mg after recovery to ≤ grade 1 Recurrence at 30 mg: Omit ponatinib Resume at 15 mg after recovery to ≤ grade 1 Recurrence at 15 mg: Discontinue ponatinib

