Other Non-Hematologic events	≥ Grade 3	Ponatinib	Omit drug and follow patient at least weekly until adverse event has resolved to grade ≤ 2, restart agent at next lower dose level. See sections 8.41 through 8.47 for guidance on other non-hematologic events

* Located at http://ctep.cancer.gov/protocolDevelopment/electronic_applications.ctc.htm

** Use the following to describe actions in the Action column:

- Omit = Treatment is not given for the day/days that are omitted and will not be made up, but treatment may resume once the adverse event has resolved as mandated in Table 8.2. For example, if treatment is omitted on Day 8, but the adverse event has resolved by Day 15, treatment may resume on Day 15.
- Hold/Delay = Treatment can be made up as part of this cycle
- Discontinue = Treatment is totally stopped

NOTE: If the patient experiences a significant adverse event requiring a dose reduction at the start of the next cycle, then the dose will remain lowered for that entire subsequent cycle. If that cycle is completed with no further adverse events >Grade 2, then the dose may be increased, at the investigator's discretion, one level at a time, in the following cycles.

NOTE: Adverse events requiring a dose-reduction step for any or all drugs beyond the two dose-reduction steps (levels -1 and -2) will be at the discretion of the treating physician, if the decision is made for the patient to be kept on study. These dose reductions must be clearly recorded in reported clinical data.

- 8.3 A new course of treatment may begin on the scheduled Day 1 of a new cycle if:
- The ANC is $\geq 1500/\mu\text{L}$;
 - The platelet count is $\geq 75,000/\mu\text{L}$;
 - Any other Ponatinib related adverse event that may have occurred has resolved to \leq Grade 1 or baseline severity.

If these conditions are not met on scheduled Day 1 of a new cycle, the subject will be evaluated at least weekly and the new cycle of treatment will not be initiated until the adverse event has resolved as described above.

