When therapy is resumed it will be considered day one of this new cycle. If Ponatinib was halted during the previous cycle and was restarted with a one-level dose reduction without requiring an interruption for the remainder of the cycle, then that reduced dose level will be initiated on Day 1 of the new cycle. **If ponatinib was omitted for the remainder of the previous cycle or if the new cycle is delayed due to adverse event newly encountered on the scheduled Day 1**, then the scheduled cycle will be started with a one-level dose reduction. If the study drug cannot be restarted within 28 days of the

scheduled Day 1 of a given cycle, the patient will be removed from study treatment and will proceed to event monitoring.

8.4 Additional adverse event guidance:

8.41 Hepatotoxicity: Iclusig can cause hepatotoxicity, including liver failure and death. Fulminant hepatic failure leading to death occurred in an Iclusig-treated patient within one week of starting Iclusig. Two additional fatal cases of acute liver failure also occurred. The fatal cases occurred in patients with blast phase CML (BP-CML) or Philadelphia chromosome positive acute lymphoblastic leukemia (Ph+ ALL). Severe hepatotoxicity occurred in all disease cohorts. Iclusig treatment may result in elevation in ALT, AST, or both. Monitor liver function tests at baseline, then at least monthly or as clinically indicated. Interrupt, reduce, or discontinue Iclusig as clinically indicated.

8.42 Pancreatitis: Clinical pancreatitis occurred in 6% (28/449) of patients (5%, grade 3) treated with Iclusig. Pancreatitis resulted in discontinuation or treatment interruption in 6% of patients (25/449). The incidence of treatment-emergent lipase elevation was 41%. Check serum lipase every 2 weeks for the first 2 months and then monthly thereafter or as clinically indicated. Consider additional serum lipase monitoring in patients with a history of pancreatitis or alcohol abuse. Dose interruption or reduction may be required. In cases where lipase elevations are accompanied by abdominal symptoms, interrupt treatment with Iclusig and evaluate patients for pancreatitis. Do not consider restarting Iclusig until patients have complete resolution of symptoms and lipase levels are less than 1.5 x ULN.

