10.0 Adverse Event (AE) Reporting and Monitoring

10.1 Adverse Event Characteristics

CTCAE term (AE description) and grade: The descriptions and grading scales found in the revised NCI Common Terminology Criteria for Adverse Events (CTCAE) version 4.0 will be utilized for AE reporting. All appropriate treatment areas should have access to a copy of the CTCAE version 4.0. A copy of the CTCAE version 4.0 can be downloaded from the CTEP web [site](http://ctep.cancer.gov/protocolDevelopment/electronic_applications/ctc.htm): (http://ctep.cancer.gov/protocolDevelopment/electronic_applications/ctc.htm)

10.11 Adverse event monitoring and reporting is a routine part of every clinical trial. First, identify and grade the severity of the event using the CTCAE version 4.0. Next, determine whether the event is expected or unexpected (see Section 10.2) and if the adverse event is related to the medical treatment or procedure (see Section 10.5). With this information, determine whether the event must be reported as an expedited report (see Section 10.). Expedited reports are to be completed within the timeframes and via the mechanisms specified in Sections 10.4. All AEs reported via expedited mechanisms must also be reported via the routine data reporting mechanisms defined by the protocol (see Sections 10.6 and 18.0).

- 10.12 Each CTCAE term in the current version is a unique representation of a specific event used for medical documentation and scientific analysis and is a single MedDRA Lowest Level Term (LLT). Grade is an essential element of the Guidelines and, in general, relates to **severity** for the purposes of regulatory reporting to NCI.

NOTE: A severe AE, as defined by the above grading scale, is **NOT** the same as serious AE which is defined in the table in Section 10.4.

- 10.13 Medical conditions/diseases present before starting study treatment are only considered adverse events if they worsen after starting study treatment (any procedures specified in the protocol). Adverse events occurring before starting study treatment but after signing the informed consent form are recorded. Abnormal laboratory values or test results constitute adverse events only if they induce clinical signs or symptoms or require therapy, and are recorded.

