13.0 Treatment/Follow-up Decision at Evaluation of Patient

- 13.1 Patients who are CR, PR, or SD will continue treatment per protocol.
- 13.2 Patients who develop PD while receiving therapy will go to the event monitoring phase.
- 13.3 Patients who go off protocol treatment for reasons other than PD will go to the event monitoring phase per Section 18.0.
- 13.4 A patient is deemed *ineligible* if after registration, it is determined that at the time of registration, the patient did not satisfy each and every eligibility criteria for study entry. The patient may continue treatment off-protocol at the discretion of the physician as long as there are no safety concerns, and the patient was properly registered. The patient will go directly to the event monitoring phase of the study (or off study, if applicable).
- If the patient received treatment, all data up until the point of confirmation of ineligibility must be submitted. Event monitoring will be required per Section 18.0 of the protocol.

- If the patient never received treatment, on-study material and the End of Active Treatment/Cancel Notification Form must be submitted. No further data submission is necessary.
- 13.5 A patient is deemed a *major violation*, if protocol requirements regarding treatment in cycle 1 of the initial therapy are severely violated that evaluability for primary end point is questionable. All data up until the point of confirmation of a major violation must be submitted. The patient will go directly to the event-monitoring phase of the study. The patient may continue treatment off-protocol at the discretion of the physician as long as there are no safety concerns, and the patient was properly registered. Event monitoring will be required per Section 18.0 of the protocol.
- 13.7 A patient is deemed a *cancel* if he/she is removed from the study for any reason before any study treatment is given. On-study material and the End of Active Treatment/Cancel Notification Form must be submitted. No further data submission is necessary.

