16.32 Definitions and Analyses of Secondary Endpoints

- 16.321 Progression-free survival time is defined as the time from registration to the earliest date of documentation of disease progression. If a patient dies without a documentation of disease progression the patient will be considered to have had disease progression at the time of their death. In the case of a patient starting treatment and then never returning for any evaluations, the patient will be censored for progression 1 day post-registration. The distribution of progression-free survival time will be estimated using the method of Kaplan-Meier (1958).
- 16.322 Survival time is defined as the time from registration to death due to any cause. The distribution of survival time will be estimated using the method of Kaplan-Meier (1958).
- 16.323 CA 19-9 response is defined to be a $\geq 50\%$ reduction from baseline. The CA 19-9 response rate will be estimated by the number of CA 19-9 responses divided by the total number of evaluable patients. A confidence interval will be calculated based on the binomial distribution.
- 16.324 Adverse Events: All eligible patients that have initiated treatment will be considered evaluable for assessing adverse event rate(s). The maximum grade for each type of adverse event will be recorded for each patient, and frequency tables will be reviewed to determine patterns. Additionally, the relationship of the adverse event(s) to the study treatment will be taken into consideration.

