16.4 Data & Safety Monitoring

16.41 The principal investigator(s) and the study statistician will review the study at least twice a year to identify accrual, adverse event, and any endpoint problems that might be developing. The Mayo Clinic Cancer Center (MCCC) Data Safety Monitoring Board (DSMB) is responsible for reviewing accrual and safety data for this trial at least twice a year, based on reports provided by the MCCC Statistical Office.

16.42 Adverse Event Stopping Rule: The stopping rule specified below is based on the knowledge available at study development. We note that the Adverse Event Stopping Rule may be adjusted in the event of either (1) the study re-opening to accrual or (2) at any time during the conduct of the trial and in consideration of newly acquired information regarding the adverse event profile of the treatment(s) under investigation. The study team may choose to suspend accrual because of unexpected adverse event profiles that have not crossed the specified rule below.

Accrual will be temporarily suspended to this study if at any time we observe events considered at least possibly related to study treatment (i.e., an adverse event with attribute specified as "possible", "probable", or "definite") that satisfy the following:

- if 4 or more patients in the first 20 treated patients (or 20% after 20 patients have been accrued) experience a Grade 4 or higher non-hematologic adverse event.

We note that we will review Grade 4 and 5 adverse events deemed "unrelated" or "unlikely to be related", to verify their attribution and to monitor the emergence of a previously unrecognized treatment-related adverse event.

- 16.5 Results Reporting on ClinicalTrials.gov: At study activation, this study will have been registered within the “ClinicalTrials.gov” website. The Primary and Secondary Endpoints (ie, “Outcome Measures”) along with other required information for this study will be reported on ClinicalTrials.gov. For purposes of timing of the Results Reporting, the initial estimated completion date for the Primary Endpoint of this study is 22 months after the study opens to accrual. The definition of “Primary Endpoint Completion Date” (PECD) for this study is the time that every patient has either completed 4 cycles of treatment or ended active treatment (whichever occurs first).
- 16.6 Inclusion of Women and Minorities
- 16.61 This study will be available to all eligible patients, regardless of race, gender, or ethnic origin.

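### Section 16.324 leaves treated but ineligible patients out of AE rates, and Section 10.13's laboratory condition makes it unclear whether asymptomatic Grade 4 chemistry events count in 16.324 and 16.42

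*Combined protocol and SAP*

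**What the plan says.** **Population.** Section 16.324 defines who contributes to AE rates: "All eligible patients that have initiated treatment will be considered evaluable for assessing adverse event rate(s"). Section 13.4 allows ineligibility to be established after registration, hence after dosing, and then requires: "If the patient received treatment, all data up until the point of confirmation of ineligibility must be submitted". The suspension rule in Section 16.42 has no eligibility condition. It acts "if 4 or more patients in the first 20 treated patients" (or 20% once 20 have been accrued) "experience a Grade 4 or higher non-hematologic adverse event" that is at least possibly related to treatment.

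**Laboratory events.** Section 10.13 states: "Abnormal laboratory values or test results constitute adverse events only if they induce clinical signs or symptoms or require therapy". Table 8.2 has a column headed as adverse events and lists laboratory changes there by grade, for example "Alanine aminotransferase increased (ALT) and/or Aspartate aminotransferase increased (AST) ≥ Grade 3". It also has rows for neutrophils, platelets and amylase. Grade 3 amylase is split by radiographic findings, but no laboratory row asks for symptoms or therapy. Lipase has no row and could fall only under "Other Non-Hematologic events". The table in Section 10.6 has neutrophil and platelet decreases graded at each evaluation. It does not contain amylase, lipase, ALT or AST. For events outside that table, Sections 10.611 and 10.612 require submission of AEs, so they depend on what counts as an AE.

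**The concern.** Estimating the adverse event profile is a secondary goal (Section 2.22), and Section 16.42 holds the only numerical safety rule. Two wordings decide what reaches them.

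First, being found ineligible does not undo exposure. A patient who took the drug is informative about its toxicity, and the plan already collects the data. As written, 16.324 and 16.42 use different safety populations.

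Second, the plan has two views of when a laboratory value is an AE, and neither 16.324 nor 16.42 says which applies. Amylase, lipase and transaminase rises are the kind of event that can be high grade without symptoms. If 10.13 governs, such an event can change or end treatment under Table 8.2 and still be absent from the AE table and the suspension count.

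**Working it through.** The plan gives no operating characteristics for the AE rates or for the suspension rule, so there is no stated figure to reproduce. The Section 16.24 power table concerns clinical benefit and is unaffected.

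**1. Eligibility restriction**

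Inputs: maximum accrual is 30, with an allowance of 3 for ineligibility, cancellation, major violation or other reasons (Section 16.22). Cancels are never treated (Section 13.7), so they are in neither safety population. Major violations are not excluded by 16.324. Treated but ineligible patients are therefore probably fewer than 3. I take 0 to 2 as likely and 3 as the extreme.

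Assumptions: all 30 are treated, 6 have a given event, and ineligibility is unrelated to having it. The all-treated rate is 6/30 = 20.0% (exact 95% interval 7.7% to 38.6%). If d patients are dropped and k of them had the event, the reported rate is (6 − k)/(30 − d), with hypergeometric probability for k.

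| Dropped | Reported rate (probability) |
|---|---|
| 1 | 6/29 = 20.7% (0.800); 5/29 = 17.2% (0.200) |
| 2 | 6/28 = 21.4% (0.634); 5/28 = 17.9% (0.331); 4/28 = 14.3% (0.034) |
| 3 (extreme) | 6/27 = 22.2% (0.499); 5/27 = 18.5% (0.408); 4/27 = 14.8% (0.089); 3/27 = 11.1% (0.005) |

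The rate can move either way, and every value lies inside the sampling interval.

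**2. Laboratory events, section by section**

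| Event | 10.13 taken literally | Table 8.2 | 10.6 | Bears on 16.42? |
|---|---|---|---|---|
| Neutrophils, platelets | AE only if symptomatic or treated | listed, no such condition | graded at each evaluation | No, hematologic |
| Amylase, ALT/AST | AE only if symptomatic or treated | listed, no such condition | not listed | Yes, at Grade 4 |
| Lipase | AE only if symptomatic or treated | general row only | not listed | Yes, at Grade 4 |

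For blood counts, 10.6 can be read as a specific instruction that overrides 10.13. For amylase, lipase and ALT/AST there is no such override, because they reach routine reporting through 10.611 and 10.612 only if they are already AEs. The plan also does not say whether omitting a dose counts as requiring therapy.

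**3. Suspension rule, hypothetical only**

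Let p be the true proportion of patients with a qualifying event and f the share of those patients whose only qualifying event is an uncounted laboratory one. The documents give neither. P(4 or more of 20) is a binomial tail at p(1 − f):

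| p | f = 0 | f = 10% | f = 25% | f = 50% |
|---|---|---|---|---|
| 10% | 0.133 | 0.099 | 0.058 | 0.016 |
| 20% | 0.589 | 0.497 | 0.352 | 0.133 |

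Only the direction is established: leaving events uncounted cannot raise this probability.

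**The case against.** **Eligibility.** The restriction drops patients, not necessarily events. In the example, the likeliest result of dropping one patient is a slightly higher rate. Eligibility is verified before registration is accepted (Section 6.3), and serious events are reported under Section 10.4 with no eligibility condition stated. All of this stands. A reader might infer that 16.324 biases toxicity downwards or weakens the suspension rule. The documents support neither: the direction is unknown, and 16.42 already counts treated patients.

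**Laboratory events.** Table 8.2 governs dose modification and need not define what is recorded, and 10.6 can settle the matter for blood counts. The values are not lost. Section 18.1 has laboratory forms, with amylase and lipase plausibly under the 'Other Laboratory' form, since the chemistry group in Section 4.0 omits both. Section 10.4 has a notification form for other Grade 4 or 5 events. The team may suspend without the rule being crossed, and the DSMB reviews safety at least twice a year. These points limit the consequence. They do not say whether the event enters the 16.324 tables or the 16.42 count.

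**Size.** A reader might use Section 8.42 to infer a large undercount. It says "The incidence of treatment-emergent lipase elevation was 41" percent, against clinical pancreatitis in 28/449 = 6.2%, a difference of 34.8 points. That inference fails. The lipase figure has no grade split and no stated denominator, absence of pancreatitis does not mean absence of symptoms or therapy, and these are earlier ponatinib data, not data from this trial.

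**Conclusion.** Both points hold as defects of wording, at minor to moderate priority.

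The eligibility restriction is small and adds nothing useful to a safety analysis. Its size rests on the 0 to 2 range inferred from the plan's allowance and on the assumed 6 events.

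The laboratory point is the more substantive. For amylase, lipase and ALT/AST, the documents do not settle whether an asymptomatic, untreated Grade 4 rise is an AE for 16.324 and 16.42, and the literal answer under 10.13 is no. Its size cannot be estimated from the documents.

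Nor do the documents show that the suspension rule must include laboratory-only events. That is a decision for the study team. What is missing is a statement of which way it was decided.

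**What to change.** - **16.324:** compute AE rates in all patients who received any ponatinib, regardless of eligibility.
- **10.13, Table 8.2 and 10.6:** reconcile them under one recording rule for AE tabulation. One example: laboratory abnormalities of CTCAE Grade 3 or higher, and those listed in 10.6, are recorded as AEs whether or not they cause symptoms or need therapy. The cut-off is the team's choice. This concerns recording only and implies no change to any dose action.
- **16.42:** have the study team state whether at least possibly related, non-hematologic laboratory events of Grade 4 or higher count towards the rule.

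The cost is a few sentences. Data on treated ineligible patients are already required up to confirmation of ineligibility, and the laboratory tests are already scheduled, with forms in 18.1. The downside is slightly more AE data entry and reported rates that may look less favourable.

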16.33 Translational Analyses

Rate of FGFR fusions and ctDNA mutations will be described, and association with confirmed tumor response and/or clinical benefit will be investigated using a Fisher's exact test. Given the small sample size, all translational analyses are

considered exploratory and no adjustment for multiplicity will be employed. One-sided p-values ≤ 0.10 are considered statistically significant throughout.

